12.6 Analysis of exploratory endpoints

Corporate Confidential Information

Corporate Confidential Information

12.7 Interim analyses

Not applicable.

12.8 Sample size calculation

12.8.1 Primary endpoint(s)

Approximately 102 subjects will be randomized in a 1:1 ratio to one of two treatment groups: Sham and PEAR-004. This sample size will provide 80% power to detect a statistically significant difference between the two groups at a 1-sided alpha=0.05 when the true mean difference is 8 points assuming SD =16 (common to the two groups). This difference is equivalent to a standardized effect size of 0.5, which is considered a moderate effect size, and is consistent with prior randomized controlled trials (RCTs) of cognitive behavioral therapy (CBT) in schizophrenia.

Table 12-1 shows the values of power for the true mean treatment difference in the range from -4 to -10.

Table 12-1 Sensitivity of power to changes in assumptions for a design with N=102 evaluable subjects

Allocation ratio	SD (common to 2 arms)	True mean difference (Δ)	True effect size (Δ/SD)	α (1-sided)	Power
1:1	16	-4	-0.25	0.05	35%
1:1	16	-6	-0.375	0.05	59%
1:1	16	-8	-0.5	0.05	81%
1:1	16	-10	-0.625	0.05	93%

13 Ethical considerations and administrative procedures

13.1 Regulatory and ethical compliance

This clinical study was designed and shall be implemented, executed and reported in accordance with the ICH Harmonized Tripartite Guidelines for Good Clinical Practice, with applicable local regulations (including European Directive 2001/20/EC, US CFR 21), and with the ethical principles laid down in the Declaration of Helsinki.

13.2 Responsibilities of the investigator and IRB/IEC

Before initiating a trial, the investigator/institution must obtain approval/favorable opinion from the Institutional Review Board/Independent Ethics Committee (IRB/IEC) for the trial protocol,

written informed consent form, consent form updates, subject recruitment procedures (e.g., advertisements) and any other written information to be provided to subjects. Prior to study start, the investigator is required to sign a protocol signature page confirming his/her agreement to conduct the study in accordance with these documents and all of the instructions and procedures found in this protocol and to give access to all relevant data and records to Novartis monitors, auditors, Novartis Quality Assurance representatives, designated agents of Novartis, IRBs/IECs, and regulatory authorities as required. If an inspection of the clinical site is requested by a regulatory authority, the investigator must inform Novartis immediately that this request has been made.

13.3 Publication of study protocol and results

The protocol will be registered in a publicly accessible database such as clinicaltrials.gov and as required in EudraCT. In addition, after study completion (defined as last patient last visit) and finalization of the study report the results of this trial will be submitted for publication and posted in a publicly accessible database of clinical trial results, such as the Novartis clinical trial results website and all required Health Authority websites (e.g. Clinicaltrials.gov, EudraCT etc.) .

For details on the Novartis publication policy including authorship criteria, please refer to the Novartis publication policy training materials that were provided to you at the trial investigator meeting or site initiation visit.

13.4 Quality Control and Quality Assurance

Novartis maintains a robust Quality Management System (QMS) that includes all activities involved in quality assurance and quality control, to ensure compliance with written Standard Operating Procedures as well as applicable global/local GCP regulations and ICH Guidelines.

Audits of investigator sites, vendors, and Novartis systems are performed by auditors, independent from those involved in conducting, monitoring or performing quality control of the clinical trial. The clinical audit process uses a knowledge/risk based approach.

Audits are conducted to assess GCP compliance with global and local regulatory requirements, protocols and internal SOPs, and are performed according to written Novartis processes.

14 Protocol adherence

This protocol defines the study objectives, the study procedures and the data to be collected on study participants. Additional assessments required to ensure safety of subjects should be administered as deemed necessary on a case by case basis. Under no circumstances including incidental collection is an investigator allowed to collect additional data or conduct any additional procedures for any purpose involving any investigational treatments under the protocol, other than the purpose of the study. If despite this interdiction prohibition, data, information, observation would be incidentally collected, the investigator shall immediately disclose it to Novartis and not use it for any purpose other than the study, except for the appropriate monitoring on study participants.

Investigators ascertain they will apply due diligence to avoid protocol deviations. If an investigator feels a protocol deviation would improve the conduct of the study this must be considered a protocol amendment, and unless such an amendment is agreed upon by Novartis and approved by the IRB/IEC and health authorities, where required, it cannot be implemented.

1.1 Scope of document

The reporting and analysis plan (RAP) documents contain detailed information to aid the production of Statistics & Programming input into the Clinical Study Report (CSR) for trial “CPEA001A12201”.

The Statistical analysis plan (SAP) describes the implementation of the statistical analysis planned in the protocol.

1.2 Study reference documentation

This SAP was created using the clinical trial protocol (version 1) dated 12-Oct-2018.

1.3 Study objectives

1.3.1 Primary objectives

Primary objectives	Endpoints related to the primary objectives

 To assess the efficacy of PEAR-004 as an adjunct to existing clinician-directed pharmacotherapy to reduce symptoms of schizophrenia. To evaluate retention to assigned study treatment. 	
 Change in total PANSS score from baseline to day 85 or last visit. Percent dropout rate.

1.3.2 Secondary objectives

Secondary objectives	Endpoints related to the secondary objectives

 To evaluate the efficacy of PEAR-004 as an adjunct to existing clinician-directed pharmacotherapy to reduce positive symptoms of schizophrenia To evaluate the efficacy of PEAR-004 as an adjunct to existing clinician-directed pharmacotherapy to reduce negative symptoms of schizophrenia. To assess safety and tolerability of PEAR-004. To evaluate the efficacy of PEAR-004 as an adjunct to existing clinician-directed pharmacotherapy to improve psychosocial functioning in patients with schizophrenia. To evaluate the efficacy of PEAR-004 as an adjunct to existing clinician-directed pharmacotherapy to reduce 	
 Change in the Positive PANSS score from baseline to day 29, day 57, and day 85 or last visit. Change in the General Psychopathology PANSS score from baseline to day 29, day 57 and day 85 or last visit. Change in the Negative PANSS score from baseline to day 29, day 57, and day 85 or last visit. Change in the Motivation and Pleasure self-report (MAP-SR) score from baseline to day 29, day 57, and day 85 or last visit. Adverse events, serious adverse events, and adverse events leading to discontinuation throughout the study.


depression symptoms in patients with schizophrenia.
 
 • To evaluate the magnitude of the effect of PEAR-004 as an adjunct to existing clinician-directed pharmacotherapy to reduce symptoms of schizophrenia. • To evaluate the response to treatment. • To evaluate patient adherence to antipsychotic medication. 	
 • Vital signs at baseline, day 85 or last visit. • InterSePT Scale for Suicidal Thinking-Plus (ISST-Plus) score at baseline, day 29, day 57, day 85, and day 115 or last visit. • Change on the World Health Organization Quality of Life (WHOQOLBREF) scale from baseline to day 29, day 57, and day 85 or last visit. • Change in the Beck Depression Inventory, Second Edition (BDI-II) total score from baseline to day 29, day 57, and day 85 or last visit. • Percentage change in PANSS score (within assigned group) from baseline to day 29, day 57, and day 85 or last visit. • Proportion of responders, defined as a reduction of at least 20% at day 85 or last visit in total PANSS score relative to baseline. • Change in antipsychotic pharmacotherapy use as measured by the Brief Medication Questionnaire (BMQ) at day 29, day 57, and day 85 or last visit.
--	--

1.3.3 Exploratory objectives

Corporate Confidential Information

Corporate Confidential Information

1.4 Study design and treatment

This is a randomized, sham controlled, rater blinded, parallel group design. Approximately 102 subjects will be randomized (with a ratio 1:1) in the following groups:

- Group A: Clinician-directed pharmacotherapy + PEAR-004.
- Group B: Clinical directed pharmacotherapy + Sham application.

An up to 28-day screening period will include standard screening assessments as defined in the assessment schedule. Eligible subjects will be randomized on day 1 into one of the treatment groups. Subjects in both groups will continue to receive their clinician-directed standard of care treatment for schizophrenia, including pharmacotherapy. Subjects in Group A will use PEAR-004 for a period of 12 weeks. Subjects in Group B will use a sham for a period of 12 weeks. Subjects will return to the clinic for outpatient visits at week 4 (day 29), week 8 (day 57), and week 12 (day 85). At each visit, standard assessments will be performed according to the assessment schedule, including PANSS, ISST-Plus, CGI, BMQ, MAP-SR, WHOQOL-BREF, BDI-II, ISI, and Adverse Events (AEs). A final follow-up visit will be performed at week 16 (day 115), including the assessments as detailed in the assessment schedule. A graphical description of the described procedure is presented in Figure 1-1.

Figure 1-1. Study design

2 First interpretable results (FIR)

Corporate Confidential Information

3 Interim analyses

Interim analyses may be conducted to support decision making concerning the current clinical study, the sponsor’s clinical development projects in general or in case of any safety concerns. In this case, the analyses as described in the sections below are conducted for the relevant endpoints.

4 Statistical methods: Analysis sets

The Full Analysis Set (FAS) population will serve as the primary population for the analysis of efficacy data in this trial. The FAS comprises all subjects to whom study treatment has been assigned by randomization and who have a baseline observation and at least one post-randomization observation for the analysis endpoint. According to the intent-to-treat principle, subjects will be analyzed according to the treatment they have been assigned to during the randomization procedure. The baseline is defined as the last measurement obtained before administration of the randomized treatment intervention (PEAR-004/Sham) on Day 1.

The Safety Set includes all randomized subjects who received the study treatment, with subjects included in the treatment group corresponding to the treatment they actually received. While no per-protocol analysis is planned, a list of protocol violators (e.g. subjects with lack of study treatment compliance change in background therapy during the trial) will be finalized prior to analysis.

The analysis sets and protocol deviation codes are related as follows:

Table 4-1 Protocol deviation codes and analysis sets

Category Deviation code	Text description of deviation	Data exclusion
COMD01	Data from the subjects acquired after this protocol deviation will be excluded from the analysis.	-

If updates to this table are needed, an amendment to the SAP needs to be implemented prior to DBL.

5 Statistical methods for Pharmacokinetic (PK) parameters

Not applicable.

6 Statistical methods for efficacy parameters

6.1 Primary objective

The primary efficacy endpoint in the study is change in total PANSS score from baseline to day 85 or last visit, analyzed using the FAS.

6.1.1 Variables

PANSS score.

6.1.2 Statistical model, assumptions, hypotheses and method of analysis

The change from baseline in total PANSS score will be analyzed using the mixed-effects model for repeated measures (MMRM) (see Mallinckrodt et al (2001)), including the fixed, categorical effects of treatment, visit (i.e., day 1, 29, 57, 85), and treatment-by-visit interaction, as well as the continuous, fixed covariates of baseline score, baseline score-by-visit interaction, and disease duration at baseline. An unstructured (UN) covariance structure will be used to model the within-patient errors. The Kenward-Roger (KR) method will be used to adjust the estimated covariance of the mean difference and the degrees of freedom.

Corporate Confidential Information

6.1.2.1 Model checking procedures

The primary MMRM model implicitly imputes missing data under a missing at random (MAR) assumption. Therefore, no explicit imputation of missing data will be done for the primary analysis approach.

Two sensitivity analyses to assess the robustness of the primary analysis to missing data results will be performed.

Corporate Confidential Information

Corporate Confidential Information

6.1.2.2 Graphical presentation of results

Because there is a temporal component throughout the data, individual plots and model adjusted mean and 95% CIs plot showing the change from baseline over time will be presented.

6.2 Secondary objectives

The secondary efficacy endpoints listed below will be analyzed separately using an MMRM analysis. The model will include the fixed, categorical effects of treatment, visit, and treatment-by-visit interaction, as well as the continuous, fixed covariates of baseline score, baseline score-by-visit interaction, and disease duration at baseline (in years).

6.2.1 Variables

The change from baseline to each post-baseline visit, which will be the dependent variable.

6.2.2 Statistical methods for analysis

The analysis strategy will be the same as for the primary outcome. The outcomes to be analyzed are:

- Change from baseline in the positive PANSS score;
- Change from baseline in the General Psychopathology PANSS score;
- Change from baseline in the negative PANSS score;
- Change from baseline in the MAP-SR score;
- Change from baseline in the WHOQOL-BREF scale;
- Change from baseline in the BDI-II total score.

In addition, the percentage change from baseline in the total PANSS score will be analyzed using an MMRM approach. Estimates of mean percentage change from baseline to each study visit with (95% CIs) will be obtained for each treatment group (i.e., $100 \times (\text{Post Baseline} - \text{Baseline}) / \text{Baseline}$).

The data from BMQ will be listed and summarized descriptively.

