Data analysis	
The change from baseline in total PANSS score will be analyzed using the mixed-effects model for repeated measures (MMRM), with fixed, categorical effects of treatment, visit, and treatment-by-visit interaction, as well as the continuous, fixed covariates of baseline score, baseline score-by-visit interaction, and disease duration at baseline. An unstructured covariance structure will be used to model the within-patient errors. The Kenward-Roger method will be used to adjust the estimated covariance of the mean difference and the degrees of freedom. Several other covariance structures will be tested if there are convergence issues in the primary analysis.
 
The primary hypothesis to be tested is that mean change from baseline in PANSS is greater with PEAR-004 than with Sham at day 85 or last visit. The primary comparison will be the contrast between treatments on day 85. The significance test will be carried out using 1-sided $\alpha=0.05$. In addition, two-sided 90% confidence intervals for the treatment mean differences, as well as individual treatment mean change from baseline values at each study visit will be constructed.
 
Two sensitivity analyses (the selection model and the pattern mixture model) will be performed to assess the robustness of the primary analysis to missing data results. The LOCF approach will also be performed to aid in the interpretation of the results from the primary analysis.

Key words	Schizophrenia, prescription digital therapeutic, cognitive behavioral therapy, smartphone app

1 Introduction

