12.5 Analysis of secondary endpoints

12.5.1 Efficacy endpoint(s)

The secondary efficacy endpoints listed below will be analyzed separately using an MMRM analysis. The change from baseline to each post-baseline visit will be the dependent variable. The model will include the fixed, categorical effects of treatment, visit, and treatment-by-visit interaction, as well as the continuous, fixed covariates of baseline score, baseline score-by-visit interaction, and disease duration at baseline (in years). The analysis strategy will be the same as for the primary outcome ([Section 12.4.2](#)). The outcomes to be analyzed are:

- change from baseline in the positive PANSS score;
- change from baseline in the General Psychopathology PANSS score;
- change from baseline in the negative PANSS score;
- change from baseline in the MAP-SR score;
- change from baseline in the WHOQOL-BREF scale;
- change from baseline in the BDI-II total score

In addition, the percentage change from baseline in the total PANSS score will be analyzed using an MMRM approach, as described in [Section 12.4.2](#). Estimates of mean percentage change from baseline to each study visit with (90% CIs) will be obtained for each treatment group.

Corporate Confidential Information

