6.2.3.2 Graphical presentation of results

Because there is a temporal component throughout the data, individual plots and model adjusted with mean and 95% CIs plot showing the change from baseline over time will be presented.

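### Do the SAP's 95% intervals for per-arm PANSS change, where the protocol has 90%, call for a change to the plan?

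*SAP*

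**What the plan says.** Protocol 12.5.1, on the per-arm percentage change in total PANSS: "Estimates of mean percentage change from baseline to each study visit with (90% CIs) will be obtained for each treatment group". SAP 6.2.2, on the same quantity, visits and type of model: "Estimates of mean percentage change from baseline to each study visit with (95% CIs) will be obtained for each treatment group". The SAP version adds only the formula for percentage change.

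A looser pair concerns the absolute change in total PANSS. The data analysis part of the protocol summary plans "two-sided 90% confidence intervals for the treatment mean differences, as well as individual treatment mean change from baseline values at each study visit". SAP 6.1.2.2 describes a figure: "individual plots and model adjusted mean and 95% CIs plot showing the change from baseline over time will be presented". SAP 6.2.3.2, under the heading for the sensitivity analysis of the primary endpoint, has nearly the same sentence, also with 95%.

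SAP 1.1 says that the SAP "describes the implementation of the statistical analysis planned in the protocol". Nothing readable in it declares or explains a different interval level. The ends of Protocol 12.4.2 and SAP 6.1.2, where the interval level for the primary analysis could well be stated, are redacted.

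**The concern.** Two documents that should agree give different confidence levels for the same estimate. The protocol's 90% also fits its design, because a two-sided 90% interval for the treatment difference corresponds to the one-sided 0.05 test. A SAP that shows 95% wherever its level can be read therefore looks like a departure nobody declared, or like template text left in place.

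The level would matter if it governed the treatment contrast. Judging the trial by a two-sided 95% interval for the difference would be stricter than the planned test and would cost power. For per-arm means, the risk is smaller: the report would show wider intervals than the protocol planned, and a reader who assumed 90% would misjudge the precision.

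**Working it through.** **Inputs.** From Protocol 12.8.1: 102 subjects randomized 1:1 (51 per arm), SD 16, true difference 8 points, one-sided alpha 0.05, power 80% in the text and 81% in Table 12-1. Interval levels: 90% in Protocol 12.5.1 and the protocol summary; 95% in SAP 6.1.2.2, 6.2.2 and 6.2.3.2.

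**1. The plan's own figure.** The SE of the difference is 16 × √(2/51) = 3.17, so 8/3.17 = 2.525. Power = Φ(2.525 − 1.645) = Φ(0.880) = 81.1%. With the noncentral t on 100 df it is 80.6%. Both agree with the stated 80% and 81%.

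**2. Width ratio.** At a given standard error, the ratio of widths is the ratio of quantiles:

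| Basis | 95% width / 90% width |
|---|---|
| Normal (1.960/1.645) | 1.192 |
| t, 100 df (1.9840/1.6602) | 1.195 |
| t, 50 df | 1.198 |
| t, 20 df | 1.209 |

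The ratio does not involve the SD, and the sample size enters only through the degrees of freedom.

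**3. Illustration in PANSS points.** Assume that the SD of 16 applies to change from baseline, with 51 per arm and a simple per-arm SE (the mixed model's SE would differ somewhat). SE = 16/√51 = 2.240. Half-widths with t on 100 df:

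- 90%: 1.6602 × 2.240 = 3.72
- 95%: 1.9840 × 2.240 = 4.44
- difference: about 0.7 points

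The documents give no SD for percentage change, so for the quantity in SAP 6.2.2 only the ratio in step 2 can be stated.

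**4. Where the level would matter.** If success were judged by a two-sided 95% interval for the treatment difference, power at 8 points would be about 71% (normal 71.4%, t 70.6%) instead of 81%. No readable SAP passage sets that level for the difference, and the protocol summary sets 90%.

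**5. Where the passages do and do not conflict.**

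- *Percentage change per arm* (Protocol 12.5.1, SAP 6.2.2): a direct conflict, same sentence and different level.
- *Absolute change per arm* (protocol summary, SAP 6.1.2.2): not a strict conflict. The protocol promises that 90% intervals will be constructed; the SAP describes a plot with 95% intervals. A report can contain both.
- *SAP 6.2.3.2 plot*: no readable protocol passage sets a level for it.
- *Treatment difference*: no readable conflict.

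**The case for a change.** The strongest case for changing the SAP is that a pre-specified reporting level should have one value. The mismatch does not depend on redacted text, and the SAP presents itself as carrying out the protocol's analysis. A programmer working from the SAP would depart from the protocol without saying so. Correcting it would take two or three edited numbers and one program parameter. Someone used to 95% in the per-arm outputs might also carry that level over to the treatment difference, where it would matter.

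What stands is that the two sentences disagree and that the readable text gives no reason. That is a fair note for whoever next edits the SAP.

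The rest is weaker. The 90% level is tied to alpha only for the treatment contrast. Per-arm means are not tested, so the one-sided 0.05 does not dictate their interval level, and the documents do not show that 95% is wrong for them. The output is not unpredictable either: analysts work from the SAP, whose readable level is 95% throughout. Asking the SAP to confirm the level for the treatment difference could be asking for text that already exists in the redacted part of 6.1.2. A low cost of editing is no reason to edit if the results are sound as they stand.

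**Conclusion.** No change to the plan follows. The discrepancy is a document-alignment slip, clear for one descriptive secondary quantity (per-arm percentage change in total PANSS) and arguable for one plot. Its whole effect is an interval about 19% to 20% wider at the same standard error, or about 0.7 points of half-width on the PANSS scale under the assumptions in step 3 (SD 16 for change, 51 per arm, simple SE).

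A correctly labelled 95% interval is as valid as a 90% one, and dividing its half-width by about 1.2 recovers the other. Point estimates, the day-85 test, alpha and power do not depend on which is shown, and a per-arm interval is not the basis for comparing the arms. Normal practice, with the level printed on each table and figure, leaves no reader misled.

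This conclusion covers per-arm results only. It rests on the treatment-difference interval staying at the two-sided 90% of the protocol summary, which nothing readable in the SAP contradicts.
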